## ABSTRACT

In the United States, patients dependent upon parenteral nutrition (PN) receive parenteral fat emulsions composed of soybean oils. Lipids are necessary in PN-dependent patients due to their high caloric value and essential fatty acid content. They have been implicated in predisposing patients to PN-associated liver disease, and children requiring prolonged courses of PN are at risk for developing PN-associated liver disease. Animal studies have shown that IV fat emulsions such as fish oil that are high in eicosapentaenic and docosahexaenoic acid reduce impairment of bile flow which is seen in cholestasis caused by conventional fat emulsions. We hypothesize that a fat emulsion comprised of omega-3 fatty acids (i.e., fish oil) such as Omegaven™ will be well tolerated and will reduce the inflammatory effect in the liver of prolonged PN exposure, with the potential of reversing any hepatic dysfunction due to PN/IFE use. By administering Omegaven™ in place of conventional phytosterol/soybean fat emulsions we may reverse or prevent the progression of PN associated cholestasis and thus allow the patient to be maintained on PN until they are able to ingest adequate nutrition enterally.

All patients in the Intestinal Rehabilitation Program at UNMC with an abnormal serum bilirubin (>2mg/dL), receiving PN and not meeting an exclusion criteria will be approached for enrollment. Upon enrollment, the PN lipid source will be switched to Omegaven, and patients will continue to be followed in standard fashion for ongoing intestinal rehabilitation. Patients will continue to have regular follow-up including laboratory evaluation at least once weekly, with periodic radiologic and endoscopic evaluation as per our standard of care. As hypertriglyceridemia is a possible side effect of Omegaven, weekly triglyceride levels will be added to regular labs. Patients will be continued on Omegaven until weaned from intravenous lipids per standard of care. Clinical data will be collected prospectively and will be compared with historical controls.

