## **Study Design**

This study will be a prospective, non-randomized, open-label study of Omegaven™ with a total enrollment of 100 patients, for provision of parenteral lipid calories. The study cohort, receiving the PN at 1g/kg/day, will be compared to historical controls at UNMC where parenteral lipid calories were provided exclusively through soybean-based formulations, as well as, assessing the study cohorts need for small bowel and liver transplantation.

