### **Side Effects (that may lead to Disruption or Discontinuation of Omegaven™):**

The infusion of Omegaven™ can lead to prolonged bleeding time and an inhibited platelet aggregation. The administration of Omegaven™ should be stopped or reduced if there is a marked increase in blood glucose levels during infusion. Undesirable effects that are seen during infusion of Omegaven™ that may also occur with conventional fat emulsions (i.e., Intralipid) include:

Slight rise in body temperature, Heat sensation and/or cold sensation, Chills, Dyspnea, Flushing or cyanosis, Lack of Appetite, nausea, vomiting, Headache, pain in chest, bone pain, Priapism, Increase/decrease in blood pressure, Anaphylactic reactions/erythema

Other expected adverse events that are common to all patients with short bowel syndrome, regardless of the type of fat emulsion they receive, include blood stream infections and re-admittance to hospital. Causes for re-hospitalization include dehydration, bloodstream infections, electrolyte abnormalities, bowel obstruction, and central venous catheter malfunction.

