## Statistical Analysis

Data from the two sets of patient population will be pooled and compared (i.e., current protocol patients prescribed Omegaven™ PN compared to historical controls where parenteral lipid calories were provided exclusively through soybean-based formulations). Potential for effect in different patient populations will be minimized by matching patients enrolled in the Omegaven™ protocol to historical controls. Frequency matching will be utilized given the difficulty of paired matching in this patient population. Specific matching criteria will include gender, age, etiology of short bowel syndrome, and severity of liver disease (parenteral nutrition- associated liver disease).

Continuous data will be expressed as mean +/- SEM. A two-way repeated measure ANOVA will be used to compare differences in the two groups with respect to changes between the Evaluation assessment and the subsequent analyses performed at Treatment and Treatment/Follow-up Assessments. Incidence of adverse events in each treatment arm will be compared using Fisher's exact test. Univariate and multivariate analysis will be used to identify baseline factors that may influence outcome. A P-value <0.05 will be considered statistically significant.

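### The only adverse-event test, Fisher's exact test, discards or mishandles repeat infections and readmissions; these should be compared as rates per person-time

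*Combined protocol and SAP*

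**What the plan says.** The Statistical Analysis section states: "Incidence of adverse events in each treatment arm will be compared using Fisher's exact test". It names no count, rate, person-time or time-to-event method for adverse events, and does not say whether incidence counts patients or events. The threshold is given as "A P-value <0.05 will be considered statistically significant", without sidedness.

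The Side Effects section says that the adverse events expected in short bowel syndrome, whichever lipid is used, "include blood stream infections and re-admittance to hospital. Causes for re-hospitalization include dehydration, bloodstream infections, electrolyte abnormalities, bowel obstruction, and central venous catheter malfunction".

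The Study Design section describes an "open-label study of Omegaven™ with a total enrollment of 100 patients". The number of historical controls is not given; the Statistical Analysis section says only "Frequency matching will be utilized given the difficulty of paired matching in this patient population".

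Exposure is open-ended. Under Duration of Therapy, treatment runs until the patient is weaned from parenteral nutrition and may go on as lipid alone. Under Discontinuation of Therapy, follow-up continues until rehabilitation is complete. The Treatment/Follow-up Period section has adverse experiences recorded throughout enrollment; no matching window is set for the controls. The Abstract includes tolerability in its hypothesis: a fish-oil emulsion "such as Omegaven™ will be well tolerated".

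**The concern.** Fisher's exact test compares two independent proportions and needs one yes/no per independent unit. Bloodstream infection and readmission can happen several times to the same patient.

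- **Per patient.** A patient with one infection and a patient with six score the same, so a higher rate shows only through patients who would otherwise have had none.
- **Per event.** Repeats in one patient are correlated, so the test's independence assumption fails and its p-value is not valid.

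Neither reading suits these events, even if follow-up and recording were identical in the two groups. At stake is whether the one named adverse-event comparison could show a real increase in the recurrent events that the protocol itself expects, in a study that hopes to show good tolerability.

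**Working it through.** The documents give no power, event rate or effect size for adverse events, so there is no planned figure to reproduce. The calculation shows how the test behaves over a range of assumptions.

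**Inputs from the documents.** Omegaven group of 100 (Study Design); significance level 0.05 (Statistical Analysis).

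**Assumptions.** 100 controls; two-sided test; equal follow-up; per-patient counts with control mean m and Omegaven mean 2m or 1.5m. Counts are Poisson (k = 0) or negative binomial with dispersion k = 1/shape.

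**Formulas.**
- Share with at least one event: 1 − exp(−m) for Poisson, otherwise 1 − (1 + k·m)^(−1/k).
- Fisher power: the binomial probabilities of all 2×2 tables with p < 0.05, summed exactly.
- Rate comparison: Wald test of the log rate ratio, variance (1/m₁ + k)/n₁ + (1/m₂ + k)/n₂.

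**Worked case: shape 2 (k = 0.5), m = 4, doubled to 8.**
- Shares: 1 − 3^(−2) = 88.9% and 1 − 5^(−2) = 96.0%. Exact enumeration gives Fisher a 61% chance of missing the doubling.
- Rate comparison: variance (0.25 + 0.5)/100 + (0.125 + 0.5)/100 = 0.01375, standard error 0.117, z = 0.693/0.117 = 5.9. It misses under 1% of the time.
- For a 1.5-fold rate (4 to 6), Fisher misses 84%. The rate variance is 0.01417, z = 0.405/0.119 = 3.4, and it misses 7%.

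**Doubled rate, 100 v 100:**

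| Counts | Control mean | Share with an event | Fisher misses | Rate comparison misses |
|---|---|---|---|---|
| Poisson | 0.5 | 39% v 63% | 9% | 2% |
| Poisson | 1 | 63% v 86% | 4% | <1% |
| Poisson | 2 | 86% v 98% | 13% | <1% |
| Poisson | 3 | 95.0% v 99.8% | 68% | <1% |
| Poisson | 4 | 98% v ~100% | 99% | <1% |
| Shape 2 | 1 | 56% v 75% | 21% | <1% |
| Shape 2 | 4 | 89% v 96% | 61% | <1% |
| Shape 2 | 6 | 94% v 98% | 81% | <1% |
| Shape 1 | 1 | 50% v 67% | 37% | 4% |
| Shape 1 | 3 | 75% v 86% | 59% | <1% |
| Shape 0.5 | 3 | 62% v 72% | 72% | 10% |

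**1.5-fold rate.** Over control means of 1–6 with Poisson, shape 2 and shape 1 counts, Fisher misses 44–100% and the rate comparison about 0–44%.

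**Two mechanisms.** In the Poisson rows, Fisher fails when nearly everyone has an event. In the shape 1 row at mean 3, it misses 59% although only 75% v 86% have an event; that loss comes from discarding repeats.

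**Short exposure.** At an assumed 2 events per patient-year over 30 days (the minimum expected need for parenteral nutrition in the Inclusion Criteria), m = 2 × 30/365 = 0.164. The Poisson shares are 1 − exp(−0.164) = 15% and 1 − exp(−0.329) = 28%. Fisher misses a doubling 46% of the time and the rate comparison 37%. Both are weak and the gap is small.

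**Why an offset is needed.** At a constant rate, observing one group twice as long gives the same counts as doubling its rate. At shape 2 and mean 4, with no true difference, a raw count comparison would then declare one more than 99% of the time, and Fisher about 39%.

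**The case against.** The strongest reply is that the size of the problem is assumed. The documents give no event rate, follow-up length or number of controls, and nothing in them predicts an increase on Omegaven. A reader might infer that nearly every patient in both groups will have an event, so that a non-significant result is almost certain. The documents do not support that: near-100% shares need roughly 3 or more events per control patient with little variation between patients, and at Poisson means of 0.5–2 Fisher detects a doubling 87–96% of the time. This part stands.

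It can also be said that the per-patient reading is itself inferred, since the unit is undefined. True, but the per-event reading is no better.

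A third reply is that safety does not rest on Fisher alone, because the Efficacy and Safety Variables are changes from baseline compared by ANOVA. That list covers nutrition, laboratory, imaging and endoscopic measures; it does not include bloodstream infections or readmissions. It is fair to add that the formal Hypothesis concerns liver enzymes and bilirubin, the primary objective is small bowel transplantation, and no section says that a non-significant Fisher test will be taken as proof of tolerability.

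Last, replacing the test with raw event counts could do harm, because follow-up differs by patient. This stands too, and the change must therefore include time at risk.

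**Conclusion.** The point holds as a weakness of the safety analysis. It does not affect the primary objective. For recurrent events, the only named test either discards repeats or breaks its own independence assumption, and the rate comparison did better in every case run.

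The size is conditional on 100 v 100 patients, equal follow-up and assumed rates. For a doubled rate, Fisher's chance of missing it runs from about 4% (Poisson, mean 1) to 99% (Poisson, mean 4), with 21–81% at gamma shape 2 and means of 1–6. For a 1.5-fold rate it is 44–100% over means of 1–6. The loss does not require near-100% shares, and it shrinks when exposure is very short. The documents do not show that a doubling would usually be missed; they show that the plan has no method that would use the repeat events if they occur.

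**What to change.** In the Statistical Analysis section:

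- Analyse bloodstream infections and readmissions separately, as event rates per person-time, by negative binomial regression with a log follow-up offset (or a rate ratio with robust variance). Report the rate ratio with a 95% CI.
- Count events and time at risk over the same defined window in the Omegaven cohort and the historical controls.
- Keep Fisher's exact test, defined on patients with at least one event, for rare or once-only events such as an allergic reaction leading to withdrawal.

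The cost is a change of wording and one extra model. The real downside is data collection: the number of events and the observation time, not just whether an event occurred, must be taken from the control charts.

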### Efficacy and Safety Variables

The efficacy and safety variables in this study will be the change from the baseline assessment to the end of follow-up assessment or end of treatment assessment for the variables listed below. The variables will be determined from: the measurement of body weight, the recording of TPN prescriptions, blood and urine analyses, radiology reports, GI exams, and possible liver biopsies.

- Parenteral Nutrient Requirements (determined from the TPN/PN prescription)
  - TPN/PN infusions (days/week)
  - TPN/PN fluid volume (cc/week)
  - TPN calories (kcal/week)
  - TPN protein (g/week)
  - TPN lipid (g/week)
  - Intravenous vitamins (type and # of infusions/week)
  - Intravenous trace elements (type and # of infusions/week)
  
- Assessment of Nutritional Status
  - Body Composition
  - Body Weight
  
  - Nutrient and Metabolic Profile (Blood analyses)
  - Vitamins- A, B12, C, D, E, folate
  - Minerals and trace elements - calcium, phosphorus, iron, selenium, zinc
  - Serum Proteins - total protein, albumin, globulin
  - Lipid profile - essential fatty acids levels
  - Citrulline, D-lactic acid
  - Serum Electrolytes – (sodium, potassium, chloride, bicarbonate, magnesium)
  
- Assessment of Hydration Status/ Renal Function (Blood analyses)
  - Blood urea nitrogen
  - Serum creatinine

- Assessment of Liver Function (Blood analyses)  
Total bilirubin, direct and indirect bilirubin, alkaline phosphatase, SGOT, SGPT, LDH.
- Assessment of Upper and Lower GI tract/Liver  
Upper and Lower endoscopy, mucosal biopsies and bacterial cultures  
Ultrasound of abdomen/Small bowel follow through, Barium enema  
Liver biopsy (based on clinical indication)

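### The named primary outcome is not carried into the analysis: one P<0.05 rule covers about 40 unranked variables with no confirmatory test identified

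*Combined protocol and SAP*

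**What the plan says.** Three parts of the combined document bear on this.

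- **Ranking of outcomes.** The last paragraph of Background and Rationale names need for small bowel transplantation as the main outcome. It makes clinical measures of PNALD and liver transplantation secondary. Objectives repeats transplantation as primary and the PNALD measures as secondary. Hypothesis, however, is framed on normalization of hepatic enzymes and bilirubin.
- **List of variables.** Efficacy and Safety Variables opens: "The efficacy and safety variables in this study will be the change from the baseline assessment to the end of follow-up assessment". It allows the assessment when treatment stops as an alternative, and then gives a flat list covering parenteral nutrition (PN) prescription, nutritional status, renal function, liver function and GI examinations. No item is marked primary, key or exploratory, and transplantation does not appear. Treatment/Follow-up Assessments repeats the PN, nutritional, renal and liver groups after baseline.
- **Analysis.** Statistical Analysis compares changes between the Omegaven cohort and historical controls by two-way repeated-measures ANOVA, without saying which variables enter it. It assigns Fisher's exact test to adverse events and adds univariate and multivariate searches for baseline factors. One rule then covers all of these: "A P-value <0.05 will be considered statistically significant". It contains no multiplicity adjustment, testing order or exploratory label, and no test for transplantation.

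**The concern.** Someone working from Statistical Analysis alone could not tell which P-value answers the trial's question. A small P for a vitamin or an electrolyte would earn the same label as one for the outcome the study was set up to evaluate. Because the ANOVA variables are not named, the choice of which results to present could also be made after the data are seen.

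The stakes are higher than usual because the comparison is open-label, non-randomized and against historical controls. Chance findings would add to any residual confounding, and the plan gives no prespecified ranking to set either apart from the main answer.

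**Working it through.** **The plan's own figure.** There is none to reproduce. The plan states no familywise error rate, number of tests or power. The only design size is 100 patients (Study Design), with no effect size, event rate or control number behind it.

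**Inputs.** The threshold is 0.05 per test (Statistical Analysis). The number of variables comes from counting the quantitative items in Efficacy and Safety Variables:

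| Group | Items |
|---|---|
| PN requirements (infusions, volume, calories, protein, lipid, IV vitamins, IV trace elements) | 7 |
| Body composition and body weight, under "Assessment of Nutritional Status" | 2 |
| "Vitamins- A, B12, C, D, E, folate" | 6 |
| "calcium, phosphorus, iron, selenium, zinc" | 5 |
| "total protein, albumin, globulin" | 3 |
| Essential fatty acids, taken as one item | 1 |
| Citrulline and D-lactic acid | 2 |
| Electrolytes | 5 |
| Blood urea nitrogen and creatinine | 2 |
| Liver blood tests (three bilirubin measures, alkaline phosphatase, SGOT, SGPT, LDH) | 7 |
| **Total** | **40** |

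**Expected false positives if every null is true:** m × 0.05 = 40 × 0.05 = 2.0. This holds at any correlation.

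**Chance of at least one, if independent:** 1 − 0.95^m = 1 − 0.95^40 = 0.87.

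**Effect of correlation.** Many of these measures are correlated, and the documents give no values, so the correlations here are assumptions. Simulating 200,000 sets of 40 equally correlated two-sided tests gives a chance of at least one false positive of about:

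- 0.74 at correlation 0.3
- 0.57 at correlation 0.5
- 0.38 at correlation 0.7

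**Sensitivity to the count.**

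- *Fewer tests.* Five items are doubtful as separate tests. Total bilirubin is the sum of direct and indirect, and globulin is normally total protein minus albumin. IV vitamins and IV trace elements are recorded partly as type. Follow-up essential fatty acids may be missing in controls, because the Treatment/Follow-up Period section calls that monitoring additional to standard. That leaves 40 − 5 = 35 tests, with 35 × 0.05 = 1.75 expected and 1 − 0.95^35 = 0.83 if independent.
- *Liver tests only.* 7 × 0.05 = 0.35 expected and 1 − 0.95^7 = 0.30 if independent.
- *More tests.* Counting the GI and liver examinations gives 46 to 48 items, with 2.3 to 2.4 expected and 0.91 if independent.

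Separate group and group-by-time terms, multiple time points, adverse event types and baseline-factor searches fall under the same rule. They are left out because their number is not given.

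**The case against.** The strongest reply has four parts.

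- **A primary outcome exists.** This is correct. A reader might infer from the flat list that the trial has no primary outcome, but Background and Rationale and Objectives both name one. Vitamin C and chloride hold no primary rank and no named secondary rank. What remains is that the ranking reaches neither the variable list nor the statistical section, and that no test is given for the outcome ranked first.
- **The plan never says that all 40 will be tested.** This is also correct. Statistical Analysis does not refer to the list, some items overlap, and the chemistries during treatment are at the investigator's discretion. Forty is one reading, which is why a range is shown. The silence does not remove the problem, because it leaves the choice of variables open.
- **Unadjusted P-values are common for safety and nutritional monitoring.** That is reasonable when such measures are labelled descriptive or exploratory. Here efficacy and safety items share one list and one significance rule, with no such label.
- **Confounding by era and selection may be the larger source of error.** This stands. The controls are only frequency-matched on four criteria, and no testing order corrects for that. It is a separate weakness and no reason to leave the significance rule open.

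**Conclusion.** The concern holds as a failure to carry the stated ranking into the analysis. Followed literally, the P<0.05 rule allows about two false significant findings if all 40 variables are tested and none truly differs (1.75 with 35 tests). The chance of at least one is 0.87 under independence and about 0.38 to 0.74 at assumed common correlations of 0.7 to 0.3. All of these are far above the nominal 0.05.

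A reader might go further and infer that the trial will very likely declare some benefit or harm even if Omegaven does nothing. The documents do not support that. It needs near-independent tests and a commitment to test the whole list; at a correlation of 0.7 the chance is below one half. The expected count of 2.0 is unaffected by correlation but still assumes that all 40 are tested and all nulls are true.

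**What to change.** In Statistical Analysis, replace the blanket rule with one that does the following:

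1. Reserves the confirmatory claim of statistical significance for the primary comparison, need for small bowel transplantation, and names its between-group test.
2. Labels all other listed variables, the adverse event comparisons and the baseline-factor analyses as exploratory, reported as estimates with 95% confidence intervals.
3. If a confirmatory claim is wanted on the liver hypothesis, names one liver measure in advance, and either tests it only after the primary succeeds or splits alpha between the two. Direct bilirubin is a natural candidate, as it already defines PNALD in Inclusion Criteria.

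The choice in step 3 is a real trade-off. No power or event rate is given for transplantation, so testing in sequence could block any liver claim. Splitting alpha avoids that but makes the primary threshold stricter.

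The cost is mostly wording, with no change to data collection or treatment. The one substantive task is defining the transplantation test, which the plan needs in any case. Fewer results can then be called significant. The change does not remove confounding from the historical controls.
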